### Phase III: Six Month Follow Up

Patients' meeting response or remission criteria will be followed monthly for up to six months by in-person visits or phone interviews. The MADRS, CGI-S and CGI-I scales will be administered at each encounter. Relapse will be defined as a MADRS score of 20 or above for two consecutive weeks. Patients who meet relapse criteria will have an early termination visit the following week and referred for standard clinical treatment.

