### **Study Overview and Hypotheses**

We propose to screen patients with bipolar depression I or II, who are already on acceptable mood stabilization. They may or may not be on antidepressants at the time of screening but subjects on antidepressants would be taken off them before completing the screening phase. Those patients who have a depression of at least moderate severity without significant symptoms of activation or mania will be started on a course of open label TMS treatment of up to 35 sessions. Safety and efficacy assessments will be done weekly. Patients will complete a course of treatment when they meet remission criteria (MADRS score < 10) or at the end of 30 treatments, whichever comes first. Patients who are still judged to be improving between treatment 25 and treatment 30 will be eligible to complete up to five additional treatments as the discretion of each site's principal investigator.

Patients who meet response criteria (MADRS score decreases by at least 50%) will complete the full course of 30 to 35 TMS sessions. Patients will be withdrawn for safety concerns, particularly the onset of activation suggestive of mania or a mixed state.

Patients who meet response or remission criteria will be followed monthly for up to six months to evaluate the durability of response. They will be on standard mood stabilizing medications and psychotherapy per their clinician's discretion.

The primary study hypotheses are:

1. TMS will provide effective antidepressant treatment in patients with bipolar depression both type I and II.
2. TMS will show a shorter time to response in bipolar depressed patients compared with the available data in unipolar depressed patients.
3. TMS can be safely given in bipolar depression without inducing a manic or mixed episode switch in patients who are receiving adequate concurrent mood stabilizing medication

The secondary hypothesis is:

1. The majority of treatment responders will show adequate durability of response with remitters showing better durability.

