### Phase II: Open Label TMS Treatment

Once study patients are on stable medication and it is confirmed that they meet the entry criteria for Phase II they will begin a standard course of five times a week TMS treatment for six weeks. They will be assessed at each treatment visit for side effects, concomitant medication use, and once per week for severity of depression and evidence of any symptoms suggestive of mania or agitation. Any suggestion of mania or activation will be assessed by the study physician who will evaluate to determine if the subject can remain in the study or needs other intervention to manage emerging symptoms.

The MADRS, the 17-item Hamilton Depression Rating Scale (HAM-D17), the Quick Inventory of Depressive Symptomatology (Self-Report) (QIDS-SR16), the

YMRS, the C-SSRS (Columbia Suicide Severity Rating Scale) and CGI-S will be performed once per week. The CGI-Improvement Scale (CGI-I) will be done weekly starting at Visit 3. Treatment will continue until remission criteria is reached (MADRS score <10) or 30 treatments have occurred, whichever comes first. If improvement is continuing between treatment 25 and 30, treatments may be extended up to 35. Patients who are discontinued due to onset of manic or mixed symptoms will be followed until resolution of these symptoms. Patients who meet response criteria (MADRS score drops by at least 50%) or remission criteria will be followed in Phase III.

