### **Inclusion and Exclusion Criteria – Phase II**

Patients must meet fulfill all of the following inclusion criteria in order to enter Phase II of the study:

1. Must be at least 18 years old.

2. Must meet **DSM-5** criteria for bipolar (either I or II) depression by clinical interview and M.I.N.I. The duration of the current depressive episode must be at least 4 weeks and no longer than 3 years in length.
3. Should have a MADRS score of at least 20 at screening, an YMRS score of less than 12 and a CGI score of at least 4.
4. Must have signed the informed consent document and have a level of understanding sufficient to provide informed consent and to communicate with the investigator and site personnel.
5. Must be on a mood stabilizer acceptable to the study physician which is consistent with their diagnosis. The mood stabilizer must be at a stable dose for at least four days before starting TMS treatment.
6. If female of childbearing potential, patients must
  - a) have a negative urine pregnancy test at screening, and
  - b) not be nursing or planning a pregnancy, and
  - c) be on a medically acceptable method of birth control acceptable to the principal investigator.

Choices of contraception that meet the study requirements are

- Intrauterine device
- Hormonal contraception (estrogen-containing birth control pills, Vaginal ring, patch, injections or implants)
- Latex condom with spermicide
- Diaphragm with spermicide
- Cervical cap with spermicide

Females of childbearing potential who are abstinent can enroll in the study.

Patients will *not* be enrolled in Phase 2 of the study if they meet any of the following exclusion criteria:

1. May not be directly affiliated with Sheppard Pratt Clinical Research Programs or be immediate family of Research Programs personnel.
2. Must not have another primary Axis I diagnosis.
3. The subject must not have stopped an antidepressant less than two weeks before starting TMS treatment or unable to discontinue antidepressant therapy.
4. Should have no previous history of psychosis or substance dependence or abuse within the six months prior to Screening

5. Presence of an Axis II disorder felt by the investigator to potentially interfere with study compliance would exclude a potential participant.
6. Should not have prior intolerance of TMS or significant lack of response to adequate trials of TMS.
7. Should not have a lifetime history of lack of response to ECT or VNS.

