## **Efficacy Measures and Safety Evaluations**

### Primary Efficacy Measure:

- Montgomery-Asberg Depression Rating Scale (MADRS)

Change from baseline to endpoint in MADRS total score will be the primary efficacy measure. The MADRS is a widely used rating scale for severity of mood related symptoms (Montgomery and Asberg, 1979). The scale consists of 10 items and ranges from 0 to 60. Higher scores denote more severe symptoms. The MADRS score (as opposed to the HAMD) is more sensitive to detect changes in the psychic rather than physical symptoms of depression.

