### **Statistical Methods**

- Sample Size

We are looking to collect sufficient data to demonstrate the efficacy and safety of TMS in bipolar depression. As this is an open label trial we will aim to treat 30 patients to achieve a reasonable sample size.

- Primary Efficacy Analysis

The primary outcome measure will be the percentage of patients who respond or remit after 30 to 35 treatments. We will subdivide patients based on the diagnosis of either bipolar I or bipolar II to compare effectiveness between those groups.

The other primary outcome will be the percentage of patients who meet criteria for onset of manic symptoms based on the YMRS. The patients will also be separated based on their diagnostic category.

- Secondary Efficacy Analysis

We will also look at the HAM-D and CGI to see the percentage of patients meeting response criteria.

For the patients meeting remission criteria, we will calculate the number of treatments required to achieve remission. Patients who only meet response criteria will be treated for 30 to 35 sessions.

Responders and remitters will also be followed for six months after the final treatment to see the durability of response. Percentage of patients' meeting relapse criteria will be calculated.

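### The only planned durability result is a fixed MADRS relapse cut-off of 20, which does not measure durability of a 50% response; a response-based result should be reported beside it

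*Combined protocol and SAP*

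**What the plan says.** Entry to follow-up depends on a relative or a low absolute score. Under Phase II: Open Label TMS Treatment: "Patients who meet response criteria (MADRS score drops by at least 50%) or remission criteria will be followed in Phase III". Remission is a score under 10: "Treatment will continue until remission criteria is reached (MADRS score <10) or 30 treatments have occurred".

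Relapse is absolute and takes no account of baseline. Under Phase III: Six Month Follow Up: "Relapse will be defined as a MADRS score of 20 or above for two consecutive weeks". The same cut-off appears under Patient Withdrawal as a ground for discontinuation.

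The cut-off equals the entry minimum. Inclusion criterion 3 reads "Should have a MADRS score of at least 20 at screening" and sets no upper limit. On the scale itself: "The scale consists of 10 items and ranges from 0 to 60".

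The secondary hypothesis (Study Overview and Hypotheses) is: "The majority of treatment responders will show adequate durability of response with remitters showing better durability". The one analysis that serves it (Statistical Methods, Secondary Efficacy Analysis) is: "Percentage of patients' meeting relapse criteria will be calculated". Adequate durability is not defined, no loss-of-response result is planned, and the analysis text does not say how remitters and other responders will be compared. Responders and remitters are "followed monthly for up to six months by in-person visits or phone interviews", with the MADRS taken at each contact.

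**The concern.** The hypothesis asks whether a response lasts. The planned percentage asks whether a patient gets back to 20. These questions coincide only for a narrow set of baselines, which has three consequences.

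- A patient can lose the response and still be counted as not relapsed.
- A patient with a high baseline can keep the response and be counted as relapsed.
- Remitters begin follow-up further from the cut-off than other responders, so the same later worsening produces fewer relapses among them.

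The first and third push the result towards the hypothesis. At stake is the secondary conclusion on durability; the primary outcomes are not affected.

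**Working it through.** The plan gives no expected relapse or durability figure, so there is none to reproduce. The check uses the plan's definitions first, then illustrations on stated assumptions.

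**1. Where the two rules disagree (documents only).** Let B be the baseline MADRS, a whole number from 20 to 60. Response holds at scores up to floor(B/2). Relapse is counted from 20. If floor(B/2) is below 19, the scores from floor(B/2)+1 to 19 are response lost, relapse not met. If floor(B/2) is 20 or more, the scores from 20 to floor(B/2) are response kept, relapse score reached.

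| Baseline | Highest score still a response | Response lost, no relapse | Response kept, at relapse score |
|---|---|---|---|
| 20 | 10 | 11-19 | none |
| 24 | 12 | 13-19 | none |
| 30 | 15 | 16-19 | none |
| 36-37 | 18 | 19 | none |
| 38-39 | 19 | none | none |
| 40 | 20 | none | 20 |
| 44 | 22 | none | 20-22 |
| 50 | 25 | none | 20-25 |

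The first band is non-empty for baselines 20-37, the rules agree at 38-39, and the second band exists from 40. At baseline 20, a responder who leaves treatment at 10 and later scores 19 has lost 9 of the 10 points gained and is not relapsed.

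**2. How common such baselines are (assumed).** The documents give no baseline distribution. With normal baselines of mean/SD 28/5, 30/6 and 32/6, rounded and truncated at 20:

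- share with B of 37 or less: 97%, 89%, 82%;
- share with B of 40 or more: 1%, 6%, 11%.

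These are shares of baselines for which a band exists, not shares of patients misclassified.

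**3. How much lost response could go uncounted (assumed).** A simulation was tuned to roughly the site's retrospective rates (26/34 = 76.5% response, 12/34 = 35.3% remission). Remitters and other responders were given the same later change, mean +5, SD 6, at a single follow-up score.

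| Baseline mean/SD | At 20 or above, all responders | 50% fall lost, all responders | Share of lost responses not counted as relapse |
|---|---|---|---|
| 26/4 | 23.5% | 58.0% | 60% |
| 30/5 | 25.5% | 47.4% | 47% |
| 34/6 | 29.3% | 40.4% | 32% |

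Over all the later-change settings tried (means 0 to 8, SD 6 or 8) the last column ran from 21% to 76%. With the +5, SD 6 change, at most about 3% of non-remitting responders were at 20 or above while still in response.

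**4. Remitters against other responders.** Remitters start at 0-9 and need a rise of at least 20 - 9 = 11. A non-remitting responder starts at 10 or more and needs at most 20 - 10 = 10. In the same simulation, with an equal later course:

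| Baseline mean/SD | Fixed 20: remitters v others | 50% rule: remitters v others |
|---|---|---|
| 26/4 | 12.5% v 32.9% | 47.8% v 66.7% |
| 30/5 | 10.8% v 38.5% | 33.2% v 60.0% |
| 34/6 | 9.8% v 44.4% | 23.0% v 54.0% |

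A hand check takes starting scores 14 and 6 and a rise of mean 5, SD 8. P(reach 20) = 1 - Φ((20 - 14 - 5)/8) = 1 - Φ(0.125) = 45%, against 1 - Φ((20 - 6 - 5)/8) = 1 - Φ(1.125) = 13%. Under the 50% rule at baseline 30 (loss from 16), the same patients give 1 - Φ(-0.375) = 65% against 1 - Φ(0.625) = 27%. The head start remains under either rule.

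**5. Why a response-based result needs a persistence rule (assumed).** Take baseline 30, end score 14, no true change and independent visit noise of SD 2 or 3. A rounded score above 15 occurs at one contact with p = 1 - Φ(1.5/SD) = 22.7% or 30.9%. Over six contacts, at least one such score has probability 1 - (1 - p)^6 = 79% or 89%. For two in a row, let a(n) be the chance of none in n contacts: a(0) = a(1) = 1 and a(n) = (1 - p)a(n-1) + p(1 - p)a(n-2). Then 1 - a(6) = 20% or 34%. This is a hard case, one point inside the limit, but it rules out requiring response at every contact.

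**The case against.** A cut-off equal to the entry minimum is a coherent definition of return to entry-level severity. The study is small and open-label, this is a descriptive secondary outcome, and the follow-up MADRS would allow loss of response to be reported anyway. All of that stands, and it is why the relapse percentage should stay. It does not make that percentage a measure of durability of response, and no other measure is planned.

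Four stronger readings are tempting and are not supported.

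- That 82-97% of patients would be misclassified. That figure only says a band exists. At baselines 36-37 the band is the single score 19.
- That sustained responders would often be called relapsed. This needs a baseline of 40 or more and a score still at 20 or above, and the definition asks for two consecutive weeks. It is possible and probably uncommon.
- That remitters and other responders cannot be compared. Being further from any threshold is part of what remission means. The gap in relapse is partly built in, which is a reason to show more than one summary.
- That a 50% rule would cure the comparison. Step 4 shows it would not.

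One adjacent point also stands: contacts are monthly, while relapse needs two consecutive weeks. The text does not say how the second week is observed.

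**Conclusion.** The mismatch holds on the documents' own definitions. For baselines 20-37 the relapse percentage can count a lost response as not relapsed. For baselines of 40 or more, about 1-11% of patients under assumed means of 28-32 and SDs of 5-6, a responder can enter Phase III already at the cut-off. A difference in relapse by remission status partly reflects starting score.

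The score bands and the 11-point and 10-point distances are exact. Every percentage for misclassification or relapse rests on assumed baselines and later change, and on one follow-up score without the two-week condition, so it illustrates direction and plausible size only. At the retrospective rates, 30 patients give about 23 responders and 50 give about 38, so a few patients classified differently would move the result visibly.

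A reader might infer that the relapse definition is wrong and should be replaced. The documents do not support that. The fault is using it as the sole durability result.

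**What to change.** In Statistical Methods, Secondary Efficacy Analysis:

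- Keep the percentage meeting the MADRS 20 relapse definition.
- Report beside it the percentage with response maintained (MADRS at or below 50% of the Phase II baseline) at month 6, and the percentage with loss of response at two consecutive monthly contacts.
- Count patients terminated early for relapse as not maintained, with a sensitivity analysis for those still at or below 50% of baseline when they left. State how missed contacts are counted.
- Give each result for all Phase III entrants, and separately for remitters and non-remitting responders. For that contrast also report change in MADRS from the end-of-treatment score.
- List separately any patient already at 20 or above on entry to Phase III.

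The early-termination wording under Phase III and Patient Withdrawal must be reconciled with response-based entry to Phase III. That is a matter for the sponsor and the investigators, and no clinical rule is proposed here.

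The cost is a little more analysis. No new visit or assessment is needed. Reported durability will probably be somewhat lower than the relapse percentage alone would suggest.

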The subject's referring clinician will be advised of their patient's participation and asked not to change medications during the open label TMS treatment. The referring clinician will be invited to follow along or transfer care to the study physician until the subject completes or discontinues open label treatment, at which point care will return to the referring clinician who will be provided with a transfer note by the study staff.

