### Concomitant Therapy

In general, concomitant medications with primarily central nervous system activity will be kept to a minimum outside of the required mood stabilizing agent. All concomitant medications taken during the study will be recorded on the case report forms. Patients will be instructed to contact the investigator or study coordinator before taking any new prescribed medications, over-the-counter medications or supplements.

Subjects will be allowed to take up to 10 mg of Ambien per night for sleep.

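### The six-month relapse percentage leaves out new treatment, mood-related admission and manic or mixed episodes, so it understates loss of benefit in Phase III

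*Combined protocol and SAP*

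**What the plan says.** **Failure event.** Phase III: Six Month Follow Up states: "Relapse will be defined as a MADRS score of 20 or above for two consecutive weeks". Visits are monthly, in person or by phone. The listed scales are the MADRS, CGI-S and CGI-I; the YMRS is not among them.

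**Analysis.** Statistical Methods gives one durability summary: "Percentage of patients' meeting relapse criteria will be calculated". No denominator is given.

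**Hypothesis.** Study Overview and Hypotheses states: "The majority of treatment responders will show adequate durability of response with remitters showing better durability". Adequate durability is not defined.

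**Treatment in follow-up.** The same section says of these patients: "They will be on standard mood stabilizing medications and psychotherapy per their clinician's discretion". The Phase I: Screening section says the referring clinician is "asked not to change medications during the open label TMS treatment", and that care goes back to that clinician once open-label treatment ends.

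**Other events.** Patient Withdrawal lists meeting the relapse criterion and onset of manic or mixed symptoms as two separate reasons for discontinuation. Serious Adverse Events includes hospitalisation. Concomitant Therapy states: "All concomitant medications taken during the study will be recorded on the case report forms".

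**The concern.** Loss of benefit after TMS can appear in ways other than a sustained high MADRS. The clinician may add treatment, the patient may be admitted, or the episode may turn manic or mixed. If this happens before the MADRS rule is met, the patient is not a relapse under the stated definition. Early intervention may also prevent the MADRS rule from ever being met. Because ratings are monthly and the rule needs two successive weeks, there is time to intervene between ratings.

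The direction is known: the sooner a worsening patient is treated, the lower the relapse percentage. There is no control arm in which the same effect could be seen. At stake is the secondary hypothesis, which is about a majority and so has a natural reference line at 50%.

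**Working it through.** **1. No figure to reproduce.** The documents give no expected relapse rate, durability threshold, or rate of treatment change, admission or switch. The retrospective counts in Background do reproduce: 45 − 4 − 5 − 2 = 34 completers, and 26/34 = 76.5% responders.

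**2. Number entering Phase III (illustration).** Statistical Methods aims to treat 30, and 30 × 26/34 = 22.9, so 23 responders. Study Population gives about 30 plus 20 over two sites, and 50 × 26/34 = 38.2, so 38 responders.

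**3. Three ways to count.** Let n be the responders, r the MADRS relapses, and e the patients with another loss-of-benefit event and no MADRS relapse. The durable share is:
- events ignored: (n − r)/n
- those patients dropped: (n − r − e)/(n − e)
- events counted as failures: (n − r − e)/n

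The stated numerator allows only the first two. The plan does not say which applies.

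**4. Direction.** If events are ignored, the failure percentage is r/n, which is below (r + e)/n whenever e > 0. If those patients are dropped, it is r/(n − e), and

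(r + e)/n − r/(n − e) = e(n − r − e) / [n(n − e)],

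which is positive whenever e > 0 and at least one patient has neither kind of event. Both readings therefore understate loss, provided the other events do represent loss of benefit.

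**5. Size.** The values of r (about 20% and 30% of n) and e (about 10%, 20% and 30%) are assumptions.

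| n | r | e | Ignored | Dropped | Counted as failures |
|---|---|---|---|---|---|
| 23 | 5 | 2 | 18/23 = 78% | 16/21 = 76% | 16/23 = 70% |
| 23 | 5 | 5 | 18/23 = 78% | 13/18 = 72% | 13/23 = 57% |
| 23 | 5 | 7 | 18/23 = 78% | 11/16 = 69% | 11/23 = 48% |
| 23 | 7 | 2 | 16/23 = 70% | 14/21 = 67% | 14/23 = 61% |
| 23 | 7 | 5 | 16/23 = 70% | 11/18 = 61% | 11/23 = 48% |
| 23 | 7 | 7 | 16/23 = 70% | 9/16 = 56% | 9/23 = 39% |
| 38 | 8 | 8 | 30/38 = 79% | 22/30 = 73% | 22/38 = 58% |
| 38 | 8 | 11 | 30/38 = 79% | 19/27 = 70% | 19/38 = 50% |

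In these rows neither reading open under the plan falls below 56%. Counting the events as failures gives less than half in three of the six rows with 23 responders, and exactly half in the last row with 38.

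**6. Precision.** Exact 95% intervals are wide: 18/23 gives 56% to 93%, and 11/23 gives 27% to 69%. The table shows a shift in the point estimate. It does not show that a majority would be statistically established or excluded.

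**The case against.** A reader might infer that the plan counts rescued, admitted or switched patients as durable responders. The documents do not say so. Durability is undefined, no denominator is given, and such patients could be treated as non-relapsed, excluded or missing. What they do establish is narrower: these events are not relapses.

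A reader might also infer that clinicians are free to give anything in follow-up. The stated discretion names only mood stabilisers and psychotherapy. Study Population bars antidepressants without saying whether that reaches Phase III. This limits the claim but does not remove it. Background describes the approved evidence base for bipolar depression as atypical antipsychotics, one of them paired with an SSRI, so new treatment need not be a stand-alone antidepressant.

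The strongest counter-argument is Patient Withdrawal. The investigator may discontinue patients for manic or mixed symptoms, suicide risk or adverse events, and they are asked to attend a termination visit with MADRS and CGI. The list includes relapse, so it reaches follow-up, and admissions are reported as serious adverse events. These patients are therefore visible in the records. But discontinuation is discretionary, a single rating a week later cannot by itself show two successive weeks, and nothing says how a withdrawn patient enters the percentage. A patient whose treatment is changed and who stays in follow-up is not flagged at all.

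Finally, the study aims to be naturalistic, and MADRS relapse regardless of later treatment is a legitimate description. That stands, and it is why the MADRS figure should be kept and supplemented.

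**Conclusion.** The point holds as a limitation of a secondary, descriptive outcome; the primary response and mania-onset outcomes are not affected. The relapse percentage captures one form of lost benefit and omits three others. Whether the affected patients remain in the denominator or are dropped, it understates loss.

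With 23 responders, 5 relapses and 5 other events, the durable share is 78% or 72% under the plan and 57% if the events count as failures. With 7 relapses and 5 events, or 5 and 7, it falls to 48%, below the majority line. With few other events the conclusion does not change.

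These sizes rest on assumed rates, on a response rate borrowed from the retrospective series, on no overlap between MADRS relapse and the other events, and on each event being a real loss of benefit. They show that the counting rule can matter, not that the hypothesis will fail.

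**What to change.** Keep the MADRS relapse percentage as defined. Beside it, pre-specify a composite with all patients entering Phase III as the denominator. A patient fails at the first of:
- MADRS relapse
- new treatment started for bipolar depression
- mood-related hospitalisation
- manic or mixed episode
- withdrawal for one of these

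Take the components from the concomitant-medication, adverse-event and withdrawal records. State the denominator of the MADRS percentage and how withdrawn patients enter it. Show the count for each component, and base the durability statement on both figures. This changes the analysis only, not patient care.

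**Cost.** About one extra table, mainly from records the protocol already requires. The reason for a treatment change must be recorded clearly enough to classify it; check this against the Phase III columns of the schedule table, which was not in the text available for this review.

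**Downsides.** Some treatment changes will not be for relapse, so the composite can overstate loss; showing both figures makes the range visible. Because the YMRS is not listed for Phase III, manic or mixed episodes would be found only through adverse-event or withdrawal records and may be under-ascertained. The report should state this as a limitation.

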### **Patient Withdrawal**

Patients will be told verbally and in the informed consent that they have the right to withdraw from the study at any time without prejudice or loss of benefits to which they are otherwise entitled.

The investigator may discontinue a patient from the study for the following reasons:

- Non-compliance with 5-day TMS treatment schedule. Patients must complete at least 4 consecutive days of treatment per week.
- It is the judgment of the investigator that the patient may be at risk for suicide
- The patient has rated a “yes” to question 4 or question 5 on the C-SSRS “Since Last Visit” version
- Patient meets relapse criteria (MADRS score  $\geq$  20 for two consecutive weeks
- Onset of manic or mixed symptoms
- Pregnancy
- Intercurrent illness, adverse event or any other reason concerning the well-being of the patient.

Patients who voluntarily withdraw from the study or who are discontinued from the study will be asked to complete an early termination visit. The early termination visit will be done one week after study withdrawal. A MADRS and CGI will be performed by the investigator. Patients will be referred back to their treating psychiatrist for standard clinical care.

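### Phase III relapse needs a high MADRS for two consecutive weeks, but the narrative schedules ratings only monthly and describes no repeat, so scheduled scores cannot establish a relapse shorter than about 30 days.

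*Combined protocol and SAP*

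**What the plan says.** Under Phase III: Six Month Follow Up, responders and remitters "will be followed monthly for up to six months by in-person visits or phone interviews". On ratings, the section says: "The MADRS, CGI-S and CGI-I scales will be administered at each encounter". It then gives the relapse rule: "Relapse will be defined as a MADRS score of 20 or above for two consecutive weeks". On what happens next: "Patients who meet relapse criteria will have an early termination visit the following week".

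Patient Withdrawal lists the same two-week rule among the reasons for discontinuation ("Patient meets relapse criteria (MADRS score" is how the item begins). It adds: "The early termination visit will be done one week after study withdrawal".

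A weekly rating rhythm is described only under Phase II: Open Label TMS Treatment. There the MADRS heads the list of scales that ends "and CGI-S will be performed once per week".

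Under Statistical Methods, Secondary Efficacy Analysis, durability is summarised by the percentage of patients "meeting relapse criteria will be calculated". No other durability statistic is named. The List of Tables names a study schedule (Table 1), but its content is not in the text available for review.

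**The concern.** The rule and the visit schedule work on different time scales. A two-week criterion needs two ratings a week or two apart, or a stated way of judging duration from one visit. The Phase III narrative gives neither. The early termination rating does not fill the gap, because it is taken after the criteria are already met. The text also does not say whether the rule means two weekly ratings or 14 full days.

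A site with a patient scoring 20 or above at a monthly contact therefore has to choose. It can wait a month for the next score, count the single score, take a history, or arrange an extra call. Each choice is compatible with the text, and they can give different rates. Two sites contribute patients. Medication and psychotherapy in follow-up are left to the clinician, so a patient treated after a high score may improve before the next monthly rating and never have two high scores.

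At stake is the evidence for the secondary hypothesis, that most responders hold their response and remitters do better. The same rule also decides who is sent to early termination.

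**Working it through.** The plan gives no relapse rate, relapse duration or sample-size calculation for this outcome, so there is no figure to reproduce. The check is visit-grid arithmetic.

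**Inputs from the document.** Monthly contacts for up to six months; MADRS threshold 20; two-week duration (Phase III). 30 patients at one site plus 20 at the other (Study Population), although Statistical Methods aims for 30. Site experience (Background): 45 treated, 34 completers, 26 responders, 12 remitters.

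**Gap between scheduled scores.** G = 365.25/12 = 30.44 days (28 to 31 by calendar month). Two consecutive scheduled scores span about 30.44/14 = 2.2 times the two-week window. They also do not show that the score stayed high in between.

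**Chance that an episode is picked up.** Assume that an episode lasts L days with MADRS at 20 or above throughout, and that its onset is uniform over the six months. Then:

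- Any single monthly score: min(1, L/G)
- Two consecutive monthly scores: min(1, max(0, (L − G)/G)) × 5/6, for L up to 2G. The 5/6 arises because an onset between months 5 and 6 cannot span two visits.
- Monthly score plus a repeat at 7 days: min(1, max(0, (L − 7)/G))
- Monthly score plus a repeat at 14 days: min(1, max(0, (L − 14)/G))

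| L (days) | One monthly score | Two monthly scores | 7-day repeat | 14-day repeat |
|---|---|---|---|---|
| 10 | 0.33 | 0 | 0.10 | 0 |
| 13 | 0.43 | 0 | 0.20 | 0 |
| 14 | 0.46 | 0 | 0.23 | 0 |
| 28 | 0.92 | 0 | 0.69 | 0.46 |
| 42 | 1.00 | 0.32 | 1.00 | 0.92 |
| 60 | 1.00 | 0.81 | 1.00 | 1.00 |

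Worked entries: at 28 days with a 7-day repeat, (28 − 7)/30.44 = 0.69. At 42 days with two monthly scores, (42 − 30.44)/30.44 = 0.38, and 0.38 × 5/6 = 0.32. At 60 days, (60 − 30.44)/30.44 = 0.97, and 0.97 × 5/6 = 0.81.

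Two monthly scores never cover an episode shorter than G. They are certain to cover one only from 2G = 60.9 days, and then only if two visits remain after onset.

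**Weight of one patient.** Response of 26/45 = 57.8% (all treated) to 26/34 = 76.5% (completers) gives 30 × 0.578 = 17.3 to 50 × 0.765 = 38.2, so about 17 to 38 patients in Phase III. One patient is 100/38 = 2.6 to 100/17 = 5.9 points. Remitters: 30 × 12/45 = 8.0 to 50 × 12/34 = 17.6. With 8 to 18 remitters, one patient is 12.5 to 5.6 points.

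**The case against.** The strongest objection is that Table 1 is unseen. Phase III ratings or unscheduled visits would be listed there, and its absence from the available text is not a fault in the plan. This stands: a reader might infer that the plan has no confirmation procedure at all, but the documents support only that the narrative describes none.

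Second, nothing forbids an extra call. The MADRS goes with every encounter and phone contact is allowed, so a site could apply the rule by arranging a repeat. That is true, but whether it happens is left to each site, and this is the source of the inconsistency.

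Third, a reader might infer that relapse will certainly be under-counted in favour of the durability hypothesis. The documents do not support that. Under-counting follows if two monthly scores are demanded. Counting one score lets in brief rises while still missing some two-week episodes, so the net direction is unknown.

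Fourth, the size is illustrative. The points per patient are simply 1/n and do not estimate how many patients would be misclassified. Episode lengths are assumed, and at 60 days two monthly scores do fairly well (0.81). Part of the advantage of a repeat at 42 days comes from allowing a rating after month 6: without the 5/6 factor, two monthly scores reach 0.38. All of this stands. So does the point that, at 14 days, even a 7-day repeat confirms only 23%, because monthly sampling is then the main limit.

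Last, this is one descriptive secondary percentage in an open-label, single-arm study, with no test and no threshold for adequate durability. That limits the importance of the point but does not remove the mismatch.

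**Conclusion.** The point holds for the narrative as written. Scheduled Phase III scores cannot establish the stated criterion for any episode shorter than about 30 days, and do so with certainty only near 60 days. This goes beyond missing detail, because applying the stated rule to the described schedule changes what counts as relapse.

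The conclusion depends on Table 1 not scheduling a repeat. The coverage probabilities rest on uniform onset, a score that stays high throughout the episode, and assumed episode lengths. The 17 to 38 patients rest on earlier site experience carrying over to this study.

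It would be wrong to read this as a threat to the trial's main results. Response, remission and the mania outcome do not use the relapse rule. Because the monthly scores are kept, a score-based rate could still be reported. It would, however, be defined after the data are seen, and patients terminated early would have no later monthly scores. The point is worth correcting and confined to the durability outcome.

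**What to change.** Add to Phase III, and refer to it from Patient Withdrawal and Secondary Efficacy Analysis:

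*Any Phase III MADRS of 20 or above, including at month 6, triggers a repeat MADRS by phone about 7 days later. Relapse is two such ratings of 20 or above. Clinical care is not delayed for the repeat. The percentage of patients with any single monthly MADRS of 20 or above is also reported, as a supporting measure.*

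This settles on the two-weekly-ratings reading. The supporting measure needs no calls. It also keeps in view a patient who is treated promptly and scores below 20 at the repeat, whom the two-rating rule would not count. If Table 1 already schedules a repeat, a cross-reference in the Phase III paragraph and a matching definition are enough.

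**Cost.** A few sentences and a small number of calls. There are at most 17 × 6 = 102 to 38 × 6 = 228 monthly ratings, and only those at 20 or above need a repeat.

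**Downsides.** A 7-day repeat counts some episodes of 7 to 13 days (about 10% of 10-day and 20% of 13-day episodes under the same assumptions). A 14-day repeat would avoid that but confirms fewer 28-day episodes (46% against 69%) and none of exactly 14 days. Monthly sampling still misses many short episodes, since only about 23% of 14-day episodes would be confirmed. The report should say so.
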